4.1 Inclusion Criteria

Potential study subjects must meet the following inclusion criteria to be enrolled in this study.

1. Men and women \geq 18 years of age in sinus rhythm
2. Able to communicate effectively with trial personnel
3. LVEF measurements obtained via 2D Echo with or without contrast or other methods (e.g. CMR, MUGA scan) obtained within 6 months prior to enrollment (Day 0)
4. Has provided signed informed consent after receiving a verbal and written explanation of this clinical trial

4.2 Exclusion Criteria

Potential study subjects who meet any of the following criteria will be excluded from the study:

1. Female subjects who are pregnant or lactating. All women of child bearing potential [WOCBP] must have a negative urine pregnancy test at screening regardless of contraceptive use history.
2. Women of child-bearing potential are excluded unless they:
 - a. are post-menopausal defined as amenorrhea \geq 12 consecutive months, **OR**
 - b. have undergone successful surgical sterilization (hysterectomy, bilateral tubal ligation or bilateral oophorectomy), **OR**

- c. have been using an adequate and medically approved method of contraception to avoid pregnancy for at least 1 month prior to DEFINITY® dose administration and be willing to continue using the same method for the duration of the study.
- 3. Current illness or pathology that would prevent undergoing investigational product administration due to a significant safety risk to the patient.
- 4. Uncontrolled arterial hypertension (defined as systolic blood pressure \geq 200 mmHg or diastolic blood pressure \geq 110 mmHg) or arterial hypotension (defined as systolic blood pressure \leq 90 mmHg).
- 5. Unstable cardiovascular status defined as:
 - a. myocardial infarction or unstable angina pectoris within 6 months prior to enrollment/DEFINITY® dose administration day
 - b. transient ischemic attack or stroke within 3 months prior to DEFINITY® dose administration
 - c. symptomatic valvular heart disease or moderate to severe stenotic valvular heart disease
 - d. clinically significant congenital heart defects
 - e. current uncontrolled cardiac arrhythmias causing symptoms or hemodynamic compromise
 - f. acute pulmonary embolus or pulmonary infarction
 - g. acute myocarditis or pericarditis
 - h. acute aortic dissection
 - i. atrial fibrillation
- 6. any major surgery within 4 weeks prior to screening
- 7. known contraindications to undergoing CMR (e.g. implanted pacemakers, cardioverter, defibrillators) or claustrophobia
- 8. participation in any investigational drug, device, or placebo study within 30 days prior to screening
- 9. known hypersensitivity to perflutren, or any of the excipients in DEFINITY®
- 10. prisoners or those who are subject to compulsory detention or involuntary incarceration for treatment of either a psychiatric or physical illness (e.g., infectious disease)

5 STUDY TREATMENT(S)

5.1 Description of Treatment(s)

5.1.1 Investigational Product

DEFINITY® is an ultrasound contrast agent consisting of phospholipids-encapsulated perfluoropropane (PFP), also known as perflutren, microspheres, which is designed to enhance echocardiographic ultrasound images. DEFINITY® (perflutren injectable suspension) will be provided in a 2-mL clear vial containing a 1.5 mL fill volume.

DEFINITY® contains no preservative. Bacterial contamination with the risk of post-administration septicemia can occur following the puncture of the elastomeric septum. It is essential to follow directions for preparation of DEFINITY® carefully and to adhere to strict aseptic procedures during preparation.

The chemical, and pharmacologic properties and formulation of DEFINITY® are described in detail in the Investigator's Brochure (IB).

5.2 Treatments Administered

All treatments will be administered as described in the Dose Preparation and Administration Guide. Appendix 2.

5.2.1 Administering Study Drug

DEFINITY® will be administered as a diluted bolus injection. 1.3 mL of activated DEFINITY® will be diluted with 8.7 mL of preservative-free saline to evenly distribute microspheres. An initial injection of up to 3 mL of diluted DEFINITY® will be administered with subsequent injections of 1 to 2 mL, as needed. Full details are available in the Dose Preparation and Administration Guide – Appendix 2.

5.3 Selection and Timing of Dose for Each Patient

All subjects will receive administration of DEFINITY® as described above and in the Dose Preparation and Administration Guide – Appendix 2.

5.4 Method of Assigning Subjects to Treatment Groups

There is only one treatment group in this study.

5.5 Blinding

This is an open-label study; therefore, no blinding procedures are required for investigators and subjects.

5.6 Concomitant Therapy

Concomitant medications will be collected from the screening visit to the 72 ± 24 hour safety follow-up phone call, and will be recorded on the eCRF.

5.7 Treatment Compliance

The investigator will comply with the protocol and all applicable regulatory requirements in assuring that the study drug is dispensed to subjects by authorized personnel only.

5.8 Packaging and Labeling

The labeling of the study drug will meet local regulatory requirements, but at a minimum will provide the investigational product name, expiry, lot number, manufacturer name and address, storage conditions, and caution warnings for investigational product use.

5.9 Storage and Accountability

The investigator is responsible for ensuring that deliveries of study drug are safely and properly received, recorded, handled, and stored in accordance with the national and/or local laws and are used in accordance with this protocol.

DEFINITY® should be stored in a refrigerator (2-8° C) upon receipt of the vials. Prior to activation, the vial should be warmed to room temperature. Following activation, DEFINITY® can be stored at room temperature (do not store above 30°C) and should be used within 12 hours of preparation. Refer to DEFINITY® Dose Preparation and Administration Guide (Appendix 2) for full storage details.

5.10 Investigational Product Retention at Study Site

The site will document the administration of the investigational product for each subject. All investigational product, used and unused, will be accounted for by a study monitor.

All unused or residual study drug must be properly destroyed at the study site in accordance with national and/or local laws and institutional policies and properly documented.

6 STUDY PROCEDURES

6.1 Screening

The timing of study procedures is provided in Appendix 1. All Screening/Baseline assessments will occur within 7 days prior to administration of study drug (Day 0).

6.2 Informed Consent

Informed consent (IC) must be obtained from each patient prior to the initiation of any study related procedures unless those procedures are considered standard of care for the diagnosis and/or treatment of the underlying disease process. The IC must meet the requirements as defined by International Conference on Harmonization (ICH) - Good Clinical Practice (GCP) guidelines, US Federal Regulations and/or conform to national or regional regulatory agency requirements, or local laws, whichever provides the greatest level of protection. Each patient must be provided, in an understandable manner, a written informed consent form (ICF) that describes the nature and duration of the study. Additionally, the patient must be allowed adequate time to consider the potential risks and benefits associated with his/her participation in the study. The IC must also contain language that allows the Sponsor (or designated representative), regulatory authorities, and the Institutional Review Board (IRB)/ Institutional Ethics Committee (IEC) direct access to the patient's medical records for the purpose of review.

In situations where study subjects are not legally competent to provide consent (i.e., cognitively incapacitated patient), written consent must be obtained from an authorized guardian or representative. In these situations, the ICF must be signed and dated by a witness and, if possible, assent must be obtained from the patient. The ICF must also be signed and dated by the individual obtaining the IC.

The Investigator, as part of the study documentation, must retain the original signed and dated ICF and must provide a signed copy to each patient or authorized representative. The Investigator will not undertake any measures specifically required only for the clinical study until valid consent has been obtained.

6.3 Medical History

A general medical history for each patient will be obtained by interview and through a review of available medical records. Data to be collected and recorded on the eCRF will include demographics (e.g. age, gender, race/ethnicity) and an overview of significant past or present illnesses, including previous administration of DEFINITY®. Known drug allergies, other allergies, or history of hypersensitivity reactions will also be recorded on the eCRF.

Information obtained via interview should be supplemented with data from hospital records or clinic charts as available.

All concomitant medications will be recorded on the eCRF. This information will be obtained by interview and through a review of available medical records.

6.4 Physical Examination

A physical examination will be performed at screening and will include height, weight, general appearance, and assessment of appearance (head, ears, eyes, nose and throat [HEENT]); neck; cardiovascular; lungs; abdomen; lymph nodes; extremities; neurological; skin; musculoskeletal; and other). All physical examination abnormalities will be recorded on the eCRF.

6.5 Vital Signs

All vital sign measurements should be obtained with the patient lying supine, having rested quietly for at least 2 minutes, as feasible. Vital signs (including heart rate, respiratory rate, and systolic and diastolic blood pressure) will be collected at the Screening visit only.

6.6 Pregnancy Test

A urine sample for pregnancy testing will be obtained for all women of childbearing potential at screening and within 24 hours prior to dosing the study drug.

6.7 Cardiac Magnetic Resonance Imaging

6.7.1 Image Acquisition

Subjects will receive a non-contrast enhanced CMR examination. MRI examinations will be performed by a qualified technologist supervised by a physician experienced with cardiac MRI. Steady-state free precession (SSFP) MRI will be performed using a 1.5 T (or above) imaging system and a standardized and harmonized pre-specified method in accordance with practice guidelines for images that are to be used for LVEF evaluation. Cardiac slices relative to single apical 2- and 4-chamber views as well as multi-slice short-axis images running from the apex to the base will be obtained for each patient. The apical 2-chamber view should be parallel to the interventricular septum and intersect the cardiac apex and mid-mitral valve; whereas, the apical 4-chamber view should be perpendicular to the interventricular septum, maximizing ventricular size, and should intersect the apex and mid-mitral valve. The left ventricular outflow tract and aorta must not be visualized in this view. Parasternal short-axis images of the left ventricle will be acquired, perpendicular to the long axis of the ventricle spanning apex to base.

Consecutive breath held short-axis cine images will be obtained with full ventricular coverage.

All images will then be transferred to an Imaging Core Laboratory for further analysis. No site analysis will be performed. Instructions for MRI data transfer and storage at the central imaging laboratory will be provided in the study Imaging Manual.

6.7.2 Imaging Core Laboratory

To identify the LV end-diastolic and end-systolic images, the full stack of short axis images will be evaluated. The LV end-diastolic image will be chosen as the phase with the largest LV blood volume. The LV end-systolic image will be chosen as the phase with the smallest LV blood volume. The Simpson's method of summation of discs will then be applied (sum over all slices of cross sectional area multiplied by the sum of the slice thickness and the inter-slice gap) to determine LV end-diastolic (LVEDV) and LV end-systolic (LVESV) volumes for entire LV. Quantification of LVEF will then be calculated based on volumes using the formula: LVEF=(LVEDV-LVESV)/LVEDV.^{4,5}

A single central MR reader will verify and correct if necessary the identification of the LV end-systolic and diastolic images provided by a trained and blinded technologist to determine the LV end diastolic and end-systolic volumes. Similarly a trained and blinded technologist will provide initial ventricular contours which will be verified and corrected if necessary by the central MR reader prior to final calculation of the volumes.

6.8 Echocardiography Imaging Procedures

6.8.1 Image Acquisition

A bedside resting transthoracic echocardiogram will be performed by personnel trained in study procedures according to standardized instructions provided here and in the study Imaging Manual. Unenhanced echocardiography will be performed in each of the standard A2C, A3C, and A4C views after optimization of these views. At least 3 consecutive cardiac cycles should be recorded in standard digital format in each view. After unenhanced imaging has been conducted, study drug will be administered as described above and in the Dose Preparation and Administration Guide. DEFINITY®-enhanced images will be obtained with low or very low MI imaging using a standardized and harmonized method consistent with practice guidelines. After study drug administration and subsequent image optimization, the same A2C, A3C, and A4C views should be obtained as with unenhanced imaging over at least 3 consecutive cardiac cycles.

Subjects will remain at the site for observation until at least 30 minutes after the end of the administration of study drug.

All images will then be transferred to an Imaging Core Laboratory for further analysis. No site analysis will be performed. Instructions for echo data transfer and storage at the central imaging laboratory will be provided in the study Imaging Manual.

6.8.2 Imaging Core Laboratory

Left ventricular end-diastolic and end-systolic volumes will be measured using the modified biplane Simpson's method in the apical 4 chamber and apical 2 chamber views. End-diastole will be identified as the frame in which the left ventricular cavity size is visually largest. End-systole will be identified as the frame in which the left ventricular cavity size is visually smallest, just before mitral valve opening. The inner contour of the LV cavity (interface between left ventricular cavity and compacted myocardium) will be traced according to the recommendations of the American Society of Echocardiography (ASE), leaving the papillary muscles and trabeculations within the cavity. Left ventricular ejection fraction will be calculated from the biplane volumes using the formula:
$$\text{LVEF} = (\text{LVEDV} - \text{LVESV}) / \text{LVEDV}.$$
⁶

A blinded echocardiography technologist at the Imaging Core Laboratory will provide an initial contour of the LV cavity for the blinded read. The blinded echocardiography readers will adjust contours based on their judgement and will provide independent LV measurements. The same method for LVEF calculation will be used for all echocardiograms, including suboptimal and non-suboptimal and both enhanced and non-enhanced.

6.9 Efficacy Assessments

Three blinded independent readers will perform all of the efficacy assessments following the methodology described in the Imaging Review Charter.

6.9.1 Primary Efficacy Assessments

The primary efficacy assessment will be the measurement of LVEF.

6.9.2 Secondary Efficacy Assessments

Secondary efficacy assessments will be the end-systolic and end-diastolic LV volumes.

6.10 Adverse Event Assessments

6.10.1 Performing Adverse Event Assessments

In this clinical trial, an AE is defined as any new untoward medical occurrence or worsening in severity or frequency of a pre-existing medical condition in a study patient, which does not necessarily have a causal relationship with investigational product. AEs occurring from the

time the informed consent is signed until the 72±24 hour telephone follow-up will be reported. Treatment-emergent adverse events (TEAEs) are a safety endpoint and are discussed in Section 8.4.1. The NCI-CTCAE version 4.0 will be utilized for Adverse Event (AE) reporting of severity by grade.

An AE can, therefore, be any unfavorable and unintended sign (including an abnormal laboratory finding, for example), symptom or disease temporally associated with the use of a medicinal (investigational or marketed) product, whether or not considered related to the medicinal (investigational or marketed) product.

Note: For this clinical trial, observations and findings (previously unknown) discovered during the procedures and medically assessed as most-likely pre-existing (e.g., myocardial wall hypokinesis, thrombus, cardiac valve deficits, and so on) will not be considered AEs and will not be reported as such in the eCRF. However, these observations and any hospitalizations/treatments required to treat the new findings will be reported elsewhere in the eCRF. Any complications resulting from the study procedures (e.g., intravenous extravasations) *will* be recorded as an AE.

A medication error is defined as any event related to the administration of a medicinal or investigational product that may cause or lead to inappropriate use or patient harm. Medication errors can be actual or potential errors and may include misuse, administration error, overdose, under-dose, or abuse. For this clinical trial, any medication errors (e.g., administration error, overdose, etc., that occur at the time of study product administration) must be recorded as an AE.

All identified AEs must be recorded and described on the appropriate AE section of the eCRF by the investigator (or designee). If known, a diagnosis should be recorded, rather than multiple individual symptoms. In addition to the event term, the following information should be captured for all AEs:

- Date (and time) of onset and resolution
- Severity of the event (see definitions below)
- Investigator's opinion of the causal relationship to study drug or comparator, procedure, or underlying disease (see definitions below)
- Treatment action taken
- Information regarding resolution/outcome

6.10.2 Timing

Timely and complete reporting of safety information helps to identify any untoward medical occurrence, thereby allowing:

- Protection of safety of study subjects,
- Greater understanding of the overall safety profile of the investigational product,
- Appropriate modification of study protocols, and
- Adherence to worldwide regulatory requirements.

Adverse event monitoring will be initiated at the time the informed consent is signed and will continue until completion of all echo assessments and patient discharge. All subjects will be followed up by telephone assessments for AEs at 72 ± 24 hours following DEFINITY® administration.

6.10.3 Severity

The Investigator (or designee) will assess the severity of the AE using the National Cancer Institute Common Terminology Criteria for Adverse Events (NCI-CTCAE) version 4.0 will be utilized for Adverse Event (AE) reporting. The NCI-CTCAE definitions of severity are below.

Grade	Degree of Severity
1	Mild, with mild or no symptoms; no interventions required
2	Moderate; minimal intervention indicated; some limitation of activities
3	Severe but not life threatening; hospitalization required; limitation of patient's ability to care for him/herself
4	Life threatening; urgent intervention required
5	Death related to adverse event

This assessment is subjective and the Investigator should use good clinical judgment to compare the reported AE to similar type experiences observed in clinical practice.

6.10.4 Relationship

The Investigator will assess the relationship of the AE to DEFINITY®. The following categories and definitions of causal relationship should be used for this study:

- **Not related:** indicates that there is little or no chance that the study treatment or procedure caused the reported AE; other conditions, including concomitant illnesses, progression or expression of the disease state, or a reaction to a concomitant medication, appear to explain the reported AE. For the purposes of determining expedited reportability, AEs categorized as unlikely related to investigational product will not be considered associated with the investigational product.
- **Possibly related:** indicates that the association of the AE with the study treatment or procedure is unknown; however, the AE is not reasonably attributed to any other condition
- **Related:** indicates that a reasonable temporal association exists between the AE and study treatment or procedure and, based upon the investigator's clinical experience, the association of the event with the study treatment seems likely

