6.10.6.2 Reporting Serious Adverse Events

All SAEs, whether related or unrelated to the investigational product, must be reported within 1 calendar day to LMI Drug Safety by confirmed facsimile transmission, email or phone. Overnight express mail may also be used in lieu of a facsimile transmission. If only limited information is initially available, follow-up reports are required. The original SAE form must be kept on file at the study site.

Collection of complete information concerning SAEs is extremely important. Thus, follow-up information that becomes available as the SAE evolves, as well as supporting documentation (e.g., hospital discharge summaries and autopsy reports), should be collected subsequently, if not available at the time of the initial report, and immediately sent using the same procedure as the initial SAE report.

The contact information for reporting SAEs and follow-up SAE information is:

Contact	Telephone Number	Fax Number	Email Address
LMI Safety	[name] + [contact]	[contact]	[contact]

If the investigator needs to discuss an SAE or any other aspect of the protocol with the Medical Monitor, s/he can be reached at the following numbers:

LMI Medical Monitor
24-Hour [contact]
[contact]

In the event of AEs that are serious, unexpected, and possibly related or related to DEFINITY® administration, LMI will contact the Investigator and will provide a MedWatch and/or Council for International Organizations of Medical Sciences (CIOMS) narrative of the case, which will include an Analysis of Similar Events. The Investigator is responsible for notifying the appropriate IRB in accordance with institutional requirements. The Investigator and IRB will determine if the IC requires revision. The Investigator should also comply with the IRB procedures for reporting any other safety information.

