9.3. Adverse Events

A treatment-emergent adverse event (TEAE) is an AE that started or worsened in severity following the start of administration of DEFINITY®. A table of AEs will be summarized for the following:

- Number of subjects having experienced at least one TEAE
- Number of subjects having experienced at least one TEAE related to DEFINITY®
- Number of subjects having experienced at least one TEAE related to study procedure
- Number of subjects having experienced at least one severe TEAE
- Number of subjects with study procedure interrupted due to a TEAE
- Number of subjects with study procedure interrupted due to a TEAE related to DEFINITY®
- Number of subjects with study procedure interrupted due to a TEAE related to the study procedure
- Number of subjects having experienced at least one serious TEAE
- Number of subjects having experienced at least one serious TEAE related to DEFINITY®
- Number of subjects having experienced at least one serious TEAE related to a study procedure
- Number of subjects having experienced at least one severe serious TEAE
- Number of subjects with study procedure interrupted due to a serious TEAE
- Number of subjects with study procedure interrupted due to a serious TEAE related to DEFINITY®
- Number of subjects with study procedure interrupted due to a serious TEAE related to the study procedure
- Number of subjects having experienced a fatal TEAE
- Number of subjects having experienced a fatal TEAE related to DEFINITY®
- Number of subjects having experienced a fatal TEAE related to the study procedure

If an AE is described as being 'related to DEFINITY®', unless otherwise stated, this will be defined as a relationship to DEFINITY® administration where the relationship is defined as either possibly related or related. If an AE is described as being 'related to study procedure', unless otherwise stated, this will be defined as a relationship to DEFINITY® enhanced echo and/or DEFINITY® administration and/or unenhanced echo and/or CMR where the relationship is defined as either possibly related or related.

This document is confidential.

A summary table of TEAEs (number and percentage of subjects who experienced an AE and number of events) grouped by primary SOC and PT will be presented for the following categories of events:

- All TEAEs
- All TEAEs related to DEFINITY®
- All TEAEs related to study procedure
- All serious TEAEs
- All serious TEAEs related to DEFINITY®
- All serious TEAEs related to study procedure

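### Protocol 6.10.4 rates relatedness to DEFINITY with definitions that also cover study procedures, so an event due only to a procedure fits no category cleanly and may be recorded as possibly DEFINITY-related

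*Protocol*

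**What the plan says.** Protocol 6.10.4 opens with a single target: "The Investigator will assess the relationship of the AE to DEFINITY". It then prescribes three categories for the study.

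- *Not related* applies where "there is little or no chance that the study treatment or procedure caused the reported AE". The alternative explanations it lists are other illness, the disease itself and other medication.
- *Possibly related* "indicates that the association of the AE with the study treatment or procedure is unknown", with the further condition that no other condition reasonably explains the event.
- *Related* starts with a temporal association to treatment or procedure, but closes with the requirement that "the association of the event with the study treatment seems likely".

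Under *Not related*, the section also says how events rated unlikely related are handled for expedited reporting. That category is not on the three-level scale.

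Protocol 6.10.1 lists what is captured for each event, including the investigator's opinion of the "causal relationship to study drug or comparator, procedure, or underlying disease", and refers forward to the same definitions.

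SAP 9.3 counts an event as related to DEFINITY if its relationship to DEFINITY administration is possibly related or related. For related to study procedure, "this will be defined as a relationship to DEFINITY® enhanced echo and/or DEFINITY® administration and/or unenhanced echo and/or CMR", at the same two levels. It plans summary lines and SOC/PT tables for both. Protocol 8.4.1 names only procedure relatedness among its tabulations. Protocol 6.10.6.2 has the sponsor issue a case narrative for events that are "serious, unexpected, and possibly related or related to DEFINITY® administration".

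**The concern.** The scale is introduced as a rating of the drug, yet two of its three definitions are met or failed on drug and procedure together. Protocol 6.10.1 does list drug and procedure as distinct items, but it borrows the same definitions, so the protocol contains no drug-only definition. Procedure complications are expected: 6.10.1 requires them to be recorded as adverse events and gives intravenous extravasation as an example.

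The study has one treatment group and no control, so investigator attribution is the main means of separating a reaction to DEFINITY from an effect of the imaging procedures. If the scale pushes procedure-only events towards *Possibly related*, the DEFINITY-related tables gain events that the investigator did not attribute to the drug. A serious event rated that way would also meet the relatedness part of the narrative trigger in 6.10.6.2.

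A second point concerns reporting. Because DEFINITY administration is one of the SAP's procedure items, no planned table shows events related to the imaging procedures alone.

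**Working it through.** The plan gives no figure to reproduce here. The check is a reading of the definitions, followed by set logic on the SAP categories.

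**Step 1. Apply 6.10.4 to an event that the investigator attributes wholly to a study procedure (for example the CMR), with no contribution from DEFINITY.**

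| Category | What it requires | Met? |
|---|---|---|
| *Not related* | Little or no chance that treatment or procedure was the cause | No: the procedure was the cause |
| *Possibly related* | Association with treatment or procedure unknown | No: the cause has been identified |
| *Related* | Temporal link, and a likely association with the study treatment | No: the last clause fails |

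None of the three categories fits. The investigator must either set aside the words about procedure and choose *Not related*, or choose the middle category. In the second case SAP 9.3 places the event in the DEFINITY-related set.

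**Step 2. Check what the SAP rule itself does.** Let A, E, U and C mean rated at least possibly related to DEFINITY administration, enhanced echo, unenhanced echo and CMR.

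- DEFINITY-related = A.
- Procedure-related = A or E or U or C.
- Possible yes/no patterns: 2^4 = 16.
- DEFINITY-related patterns: 2^3 = 8.
- Procedure-related patterns: 16 − 1 = 15.
- In both sets: 8. DEFINITY-related only: 8 − 8 = 0.
- Procedure-related but not DEFINITY-related: 15 − 8 = 7.

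The DEFINITY-related set therefore lies wholly inside the procedure-related set. The reverse is not true: the 7 patterns with E, U and/or C but not A stay outside the DEFINITY-related set. These are logical patterns, not expected event frequencies.

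**Step 3. Ask how many procedure-only events could be exposed.** Under SAP 9.3 a TEAE must start or worsen after DEFINITY administration begins. Unenhanced echo comes before dosing (protocol 6.8.1). CMR may be done up to 30 days either side of Day 0, while event collection ends at the telephone call, at most 72 + 24 = 96 hours (4 days) after dosing. A reaction to a CMR done well before dosing, or after the call, would largely fall outside the TEAE tables.

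**Step 4. Scale.** If all 150 planned subjects were dosed, one subject moved wrongly into the DEFINITY-related count would change that incidence by 1/150 = 0.67 percentage points. This is a unit of measurement, not an estimate. The documents give no expected number of procedure-only events and no expected DEFINITY-related incidence.

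**The case against.** The strongest defence is that the words about treatment or procedure form one generic scale, to be read against whichever item is being rated. Section 6.10.1 lists drug and procedure as distinct opinions, and the SAP's four named items imply a separate relationship entry for each. On that reading a CMR-only event is rated against CMR and is *Not related* to DEFINITY administration. This is plausible and it limits the problem. It does not remove it, because the case report form is not among the documents and 6.10.4 names DEFINITY as the only target.

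The SAP composite can also be defended. The protocol treats extravasation as a procedure complication, and 8.4.1 names only procedure relatedness. Taking DEFINITY administration out of the composite would drop drug-only events from the one relatedness tabulation the protocol names. That stands, and the composite should be kept.

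On reporting, all SAEs go to the sponsor whatever their relatedness, so any residual error would be towards over-reporting.

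A reader might infer that the two sets of tables merge, that the SAP counts procedure-only events as DEFINITY-related, or that a procedure-only rate cannot be obtained. Step 2 shows that the first two do not follow. On the third, because the sets are nested, subtracting DEFINITY-related from procedure-related events gives the procedure-only event count. Subtracting subjects gives those with a procedure-related TEAE and no DEFINITY-related one. The figure is not planned as a row, but it can be derived.

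**Conclusion.** The point holds as a wording error in the causality scale. Section 6.10.4 states a drug rating but defines it on drug and procedure combined, and a procedure-only event fits none of its categories. The consequence is a possible misclassification when the investigator makes the rating, which SAP 9.3 would then carry into the DEFINITY-related tables. It is not a rule of the analysis.

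Its size cannot be estimated from the documents. It depends on how investigators read 6.10.4, on whether the case report form has separate items, and on how many procedure-only events are treatment-emergent; the last number is probably small. A statement that the trial will overstate the DEFINITY-related rate by some percentage would rest on assumed counts and is not supported.

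The SAP nesting is real but one-way, and matters only for presentation. No efficacy conclusion is affected.

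**What to change.** In protocol 6.10.4:

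- Make each definition refer only to the component being rated. For DEFINITY, delete the words that add the procedure.
- State that the same scale is applied separately to DEFINITY administration, enhanced echo, unenhanced echo and CMR, as SAP 9.3 implies, and confirm that the case report form has these four items. Align 6.10.1 with this.
- Reconcile the reference to an unlikely-related category with the three-level scale.

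In SAP 9.3, keep the composite procedure-related category so that it still matches protocol 8.4.1. Add one row for TEAEs related to enhanced echo, unenhanced echo and/or CMR but not to DEFINITY administration.

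The cost is minor wording changes and one table row. There is no effect on study procedures or sample size. If the four items are already collected, no new data are needed.
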